8.3 Unblinding Procedures (prior to update #02)

As of 10/01/16, the study was redesigned from a double-blind placebo controlled study to an open label single arm study of efatutazone, due to slow accrual to the trial. Therefore, on 10/01/16 the study was unblinded and all participants were placed on open label efatutazone.

9.0 ADVERSE EVENTS

The prompt reporting of adverse events is the responsibility of each investigator engaged in clinical research, as required by Federal Regulations. Adverse events must be described and graded using the terminology and grading categories defined in the NCI's Common Terminology Criteria for Adverse Events (CTCAE), Version 4.0. However, CTCAE v5.0 must be used for serious AE reporting through CTEP-AERS as of April 1, 2018. The CTCAE is available at <http://ctep.cancer.gov/reporting/ctc.html>. Attribution to protocol treatment for each adverse event must be determined by the investigator and reported on the required forms, using the codes provided.

9.1 Routine adverse event reporting

Adverse event data collection and reporting, which are required as part of every clinical trial are done to ensure the safety of patients enrolled in the studies as well as those who will enroll in future studies using similar agents. Adverse events are reported in a routine manner at scheduled times according to the study calendar in [Section 5.0](#). For this trial, Rave is used for routine AE reporting.

Solicited Adverse Events: The following adverse events are considered "expected" and their presence/absence should be solicited, and severity graded, at baseline and for each cycle of treatment.

CTCAE v4.0 Term	CTCAE v4.0 System Organ Class (SOC)
Neutrophil count decreased	Investigations
Anemia	Investigations
Edema limbs	General Disorders
Weight gain	Investigations
Pleural Effusion	Respiratory disorders
Pericardial Effusion	Cardiac disorders
Cholesterol high	Investigations
Hypertriglyceridemia (See Section 5.0 , Footnote "5").	Investigations
Fatigue	General Disorders

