5.0 STUDY CALENDAR

Laboratory and clinical parameters during treatment are to be followed using individual institutional guidelines and the best clinical judgment of the responsible physician. It is expected that patients on this study will be cared for by physicians experienced in the treatment and supportive care of patients on this trial.

Pre-Study Testing Intervals

- To be completed \leq 14 DAYS before registration: All laboratory studies, history and physical.
- To be completed \leq 28 DAYS before registration: Any imaging modality which is utilized for tumor measurement per protocol.
- To be completed \leq 42 DAYS before registration: Any baseline exams used for screening, or any imaging of any type which is not utilized for tumor measurement.

	Prior to Registration *	Days 1 (+/- 4 days) of each cycle through Cycle 4; then Day 1 (+/- 7 days) of every odd numbered cycle for Cycle 5 and beyond	Weeks 2 and 3 (+/- 2 days) of Cycle 1	Post treatment follow up***	At PD, withdrawal, or removal****
Tests & Observations					
History and physical, weight, PS	X	X	X	X	X
Height	X				
Pulse, Blood Pressure	X	X	X		
Adverse Event Assessment		X	X		X
Registration Fatigue/Uniscale Assessment	X(1)				
Laboratory Studies					
Complete Blood Count, Differential, Platelets	X	X			
Creatinine,	X	X			
Albumin, glucose	X	X			
AST, ALT, Alk. Phos., Bili	X	X			
Fasting Triglycerides, total cholesterol		X(5)			
Serum or Urine HCG	X(2)				
Staging					
Central pathology review for eligibility	X(3)				
Tumor Measurement	X	A		X	
CT/MRI chest/abdomen/pelvis	X(4)	A		A	
A091202-ST1 Correlative studies: For patients who consent to participate					
Archival block OR slides	X				

- * Labs completed prior to registration may be used for day 1 of cycle 1 tests if obtained \leq 14 days prior to treatment.
- *** For patients who are removed from protocol therapy for reasons other than progression: Physical examination and staging scans are required every 12 weeks (+/- 7 days) (after the end of treatment) until disease progression. On completion of study treatment, all patients are followed for survival only every 6 months (+/- 30 days) until death or a maximum follow-up of 5 years. See also [Section 12.0](#).
- **** Visit and AE assessment should be completed 4 weeks (+/- 7 days) after completion of protocol therapy
 - 1 To be completed after pre-registration and prior to registration, see [Appendix I](#).

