 - 2 For women of childbearing potential (see [Section 3.3](#)). Must be done \leq 7 days prior to registration and \leq 7 days prior to re-registration at crossover.
 - 3 See [Sections 4.5](#) and [6.1](#).
 - 4 Baseline scans can include either: 1) a CT, spiral CT, or MRI, or 2) an FDG-PET scan and diagnostic CT performed with both IV and oral contrast, and the CT acquired with 5 mm or less slice thickness. If a bone scan is used for baseline scan, please note in ECRF, but bone scans are not mandatory. Documentation (radiologic and pathology report and clinic note) of the diagnosis scan must be submitted.
 - 5 Fasting triglycerides and total cholesterol will be done on Day 1 of Cycles 3 and 6 (+/- 7 days).
- A Every 6 weeks (approximately every 2 cycles) through 24 weeks, and then every 12 weeks (approximately every 4 cycles) after week 24 until evidence of progression or relapse. Scans may be done up to 7 days prior to beginning a cycle. Confirmatory scans should also be obtained at least 4 weeks following documentation of objective response (see [Section 11.0](#)).
If the baseline scans were a CT or MRI and bone scan, follow-up bone scans are required only for patients with bone metastases as the only site of evaluable disease, and are optional for other patients. **Response assessment should include assessment of all sites of disease and use the same imaging method as was used at baseline.** Documentation (radiologic and clinic note) must be provided at progression of disease.

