7.0 TREATMENT PLAN/INTERVENTION

Protocol treatment is to begin ≤ 7 days from registration.

Patients are permitted to have a new cycle of treatment delayed up to 7 days for major life events (e.g., serious illness in a family member, major holiday, vacation that cannot be rescheduled) without this being considered a protocol violation. Documentation to justify this delay should be provided.

Patients will receive efatutazone, 0.5mg orally twice daily. Each cycle is 21 days (3 weeks).

If at reimaging there is no evidence of disease progression, and the patient is tolerating therapy, then the patient will continue to remain on treatment until progression.

A091202 dose table:

Agent	Dose	Route	Day	ReRx
Efatutazone	0.5 mg	PO	BID	Every 21 days*

*Taken continuously with no break between cycles

Efatutazone tablets are to be self-administered PO BID, with or without food. The intended dosing schedule for efatutazone dosing is every 12 hours. However, dosing may occur within ± 2 hours of the scheduled administration time.

Treatment is to continue until disease progression or unacceptable adverse event. After disease progression or unacceptable adverse event, patients will be followed for a maximum of 5 years, as in [Section 5.0](#).

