8.2.5 Metabolism and nutrition disorders

For **grade 3 or 4 hypertriglyceridemia** that has physiologic or life-threatening consequences, omit efatutazone until physiologic or life-threatening consequences have resolved, then resume at same dose. If grade 3 or 4 hypertriglyceridemia is based on the numeric value and there are no physiologic or life-threatening consequences, do not interrupt drug.

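### Section 9.1 asks for solicited events to be graded at baseline, but no lipid draw is mandated before treatment: a clear mismatch for Cholesterol high, an arguable one for Hypertriglyceridemia

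*Combined protocol and SAP*

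**What the plan says.** Section 9.1 gives a list of nine solicited CTCAE terms and says of them that "their presence/absence should be solicited, and severity graded, at baseline and for each cycle of treatment". *Cholesterol high* stands in the list without a qualifier. *Hypertriglyceridemia* carries a cross-reference to footnote 5 of the study calendar.

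In the Section 5.0 calendar, the row "Fasting Triglycerides, total cholesterol" is blank in the pre-registration column. Its only mark is in the on-treatment column and refers to footnote 5: "Fasting triglycerides and total cholesterol will be done on Day 1 of Cycles 3 and 6", with a window of 7 days either side. The blood count, creatinine, albumin, glucose and liver tests are all marked before registration. The pre-study intervals above the table place "All laboratory studies, history and physical" within 14 days before registration.

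No other section adds a baseline lipid value. The eligibility laboratory values in Section 3.3.9 include no lipids, and the nursing guidelines in Section 10.1.1 refer back to the protocol for lipid monitoring.

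On use of the data, Section 9.0 states: "Attribution to protocol treatment for each adverse event must be determined by the investigator". Section 13.3 summarises maximum grade per event type and the frequency of grade 3 or higher events, neither with reference to baseline.

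**The concern.** Lipid elevation is an expected effect of this drug. Section 8.1.7 calls it a known side effect, and Section 10.1 lists both hypercholesterolemia and hypertriglyceridemia among the adverse drug reactions. Adverse event rates are part of the secondary objective in Section 2.2. Since the change to a single arm (Sections 1.6 and 8.3) there is no concurrent comparison, so each patient's own pre-treatment value is the natural reference within the trial.

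A site that follows the calendar exactly need not have that value. An abnormal result at Cycle 3 may then be drug effect, pre-existing elevation or both, and the investigator must attribute it without the most useful piece of information.

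**Working it through.** The plan states no figure to reproduce. The check compares Section 9.1 with the calendar and adds simple cycle arithmetic.

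**1. Which solicited terms need a laboratory test, and does the calendar supply a baseline?**

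| Term | Test | Marked before registration? |
|---|---|---|
| Neutrophil count decreased | Blood count | Yes |
| Anemia | Blood count | Yes |
| Cholesterol high | Fasting lipids | No |
| Hypertriglyceridemia | Fasting lipids | No |

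So 2 of the 4 laboratory-based terms have a mandated baseline test. The number of mandated pre-treatment lipid values is 0. This does not depend on how the table was extracted, because footnote 5 states the lipid schedule in words.

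**2. Could baseline mean Cycle 1 Day 1?** The adverse event row also has no pre-registration mark, so baseline grading might be done on the first treatment day. Footnote 5 mandates no lipids then either.

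**3. Does the 14-day line add a lipid test?** It sets the timing of tests done before registration. The lipid row is not marked as one of them, and footnote 5 places lipids at Cycles 3 and 6.

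**4. When is the first mandated value?** Section 7.0 sets 21-day cycles, so Cycle n Day 1 = 1 + 21 × (n − 1).
- Cycle 3 Day 1 = 1 + 21 × 2 = day 43, which is 42 days after a first dose on day 1.
- With the footnote 5 window: 42 − 7 = 35 and 42 + 7 = 49 days.
- Section 7.0 also lets a new cycle start up to 7 days late for major life events. One full delay moves the nominal time to 42 + 7 = 49 days and the late edge to 49 + 7 = 56 days. The 35 to 49 range therefore assumes no delay.

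**5. How much drug has been scheduled by then?** Section 7.0 states: "Patients will receive efatutazone, 0.5mg orally twice daily". At two doses a day, with no holds or delays, this is 42 × 2 = 84 doses (35 × 2 = 70 to 49 × 2 = 98).

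**6. Can history replace the value?** Only in part. Section 8.2.5 has a provision that begins "If grade 3 or 4 hypertriglyceridemia is based on the numeric value" and covers patients without clinical consequences. A severe grade can therefore rest on a number that history would not reveal.

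**The case against.** The strongest reply concerns the pointer on Hypertriglyceridemia. It can be read as a term-specific rule that this event is graded when footnote 5 produces a value. On that reading no baseline triglyceride grade is asked for, and most of the conflict for that term disappears. This stands as a fair reading, so the mismatch is firm only for Cholesterol high. That term shares the same calendar row and the same footnote sentence, so its missing pointer may be a clerical omission. On either reading, no baseline value is mandated.

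Second, Section 9.1 also says that routine reporting follows the study calendar. A site could record known hyperlipidemia from the mandated history and grade lipids when a draw occurs. Some sites may order a baseline panel because Section 9.1 prompts it. This softens the problem but leaves collection to local habit.

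Third, little in the plan turns on it. Section 8.2.5 does not interrupt the drug for purely numeric grade 3 or 4 hypertriglyceridemia, and the Section 13.3 summaries ignore baseline. Because lipid elevation is a listed reaction, an investigator can attribute an event as at least possible without a baseline value. All of this stands, and it keeps the point small.

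A reader might go further and infer that attribution is impossible, that the lipid event rates will be materially wrong, or that the stopping rule in Section 13.6 is compromised. The documents do not support this. They give no rate of pre-existing lipid abnormality, so no misclassification rate and no effect on the rule can be derived.

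**Conclusion.** The point holds as a minor but real inconsistency between Section 9.1 and the calendar, and is worth considering. It is clear for Cholesterol high and arguable for Hypertriglyceridemia. No lipid value is mandated before treatment. The first comes nominally 42 days after the first dose (35 to 49 with the window, later with a permitted cycle delay).

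The consequence is that, without a control arm, pre-existing elevation cannot reliably be separated from drug effect for two secondary safety terms. Attribution remains possible but is weaker than it need be. The primary endpoint is unaffected.

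The conclusion assumes 21-day cycles starting with a first dose on day 1 and a site that collects only what the calendar mandates. It would be wrong to read it as saying that both terms are in outright contradiction with the calendar, because the pointer leaves room for the other reading of Hypertriglyceridemia.

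**What to change.** 1. In the Section 5.0 calendar and footnote 5, add a fasting lipid draw (triglycerides and total cholesterol) before the first dose at Cycle 1 Day 1, or with the pre-registration bloods.
2. In Section 9.1, attach the footnote 5 pointer to Cholesterol high as well, so that both lipid terms follow the same draws, including the new baseline one.
3. In Section 13.3, show baseline grade beside maximum grade for these two terms. Without this step the new draw helps attribution but changes no planned summary.

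The cost is one fasting lipid panel per new patient, on blood already being drawn, and a fasting instruction. Section 13.5 allows up to 28 efatutazone patients, 3 of them already enrolled, so a Cycle 1 Day 1 draw means at most about 28 − 3 = 25 panels. A pre-registration draw would add patients screened but not registered, a number the documents do not give. The text changes are the calendar row with footnote 5, one pointer in Section 9.1 and one sentence in Section 13.3.

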9.2 CTCAE Routine Study Reporting Requirements

***Combinations of CTCAE Grade & Attribution Required for Routine AE Data Submission on Case Report Forms (CRFs)**

Attribution	Grade 1	Grade 2	Grade 3	Grade 4	Grade 5
Unrelated			a	a	a
Unlikely			a	a	a

Possible		a	a, b	a, b	a, b
Probable		a	a, b	a, b	a, b
Definite		a	a, b	a, b	a, b

- a) Adverse Events: Other CRF - Applies to AEs occurring between registration and within 30 days of the patient's last treatment date, or as part of the Clinical Follow-Up Phase.
- b) Adverse Events: Late CRF - Applies to AEs occurring greater than 30 days after the patient's last treatment date.

9.3 Expedited adverse event reporting (CTEP-AERS)

Investigators are required by Federal Regulations to report serious adverse events as defined below. Alliance investigators are required to notify the Alliance Central Protocol Operations Program Office, the Study Chair, and their Institutional Review Board if a patient has an adverse event requiring expedited reporting. All such events must be reported in an expedited manner using the NCI Adverse Event Expedited Reporting System (CTEP-AERS). The descriptions and grading scales found in the revised NCI Common Terminology Criteria for Adverse Events (CTCAE) version 5.0 will be utilized for AE reporting beginning April 1, 2018. All appropriate treatment areas should have access to a copy of the CTCAE version 5.0. A copy of the CTCAE version 5.0 can be downloaded from the CTEP web site http://ctep.cancer.gov/protocolDevelopment/electronic_applications/ctc.htm.

The Alliance requires investigators to route all expedited adverse events through the Alliance Central Protocol Operations Program Office for Alliance-coordinated studies. **Be sure to read this entire protocol section**, as requirements are described in both the table and bullet points following the table. The bullet points (additional instructions or exclusions) are protocol specific and in the case of a conflict, the additional instructions or exclusions supersede the table.

9.3.1 Late Phase 2 and Phase 3 Studies: Expedited Reporting Requirements for Adverse Events that Occur on Studies under an IND \leq 30 Days of the Last Administration of the Investigational Agent/Intervention ¹

FDA REPORTING REQUIREMENTS FOR SERIOUS ADVERSE EVENTS (21 CFR Part 312)

NOTE: Investigators **MUST** immediately report to the sponsor (NCI) **ANY** Serious Adverse Events, whether or not they are considered related to the investigational agent(s)/intervention (21 CFR 312.64)

An adverse event is considered serious if it results in **ANY** of the following outcomes:

- 1) Death
- 2) A life-threatening adverse event
- 3) An adverse event that results in inpatient hospitalization or prolongation of existing hospitalization for \geq 24 hours
- 4) A persistent or significant incapacity or substantial disruption of the ability to conduct normal life functions
- 5) A congenital anomaly/birth defect.
- 6) Important Medical Events (IME) that may not result in death, be life threatening, or require hospitalization may be considered serious when, based upon medical judgment, they may jeopardize the patient or subject and may require medical or surgical intervention to prevent one of the outcomes listed in this definition. (FDA, 21 CFR 312.32; ICH E2A and ICH E6).

ALL SERIOUS adverse events that meet the above criteria **MUST** be immediately reported to the NCI via CTEP-AERS within the timeframes detailed in the table below.

Hospitalization	Grade 1 Timeframes	Grade 2 Timeframes	Grade 3 Timeframes	Grade 4 & 5 Timeframes
Resulting in Hospitalization \geq 24 hrs	10 Calendar Days			24-Hour; 5 Calendar Days
Not resulting in Hospitalization \geq 24 hrs	Not required		10 Calendar Days	

Expedited AE reporting timelines are defined as:

- o “24-Hour; 5 Calendar Days” - The AE must initially be reported via CTEP-AERS \leq 24 hours of learning of the AE, followed by a complete expedited report \leq 5 calendar days of the initial 24-hour report.
- o “10 Calendar Days” - A complete expedited report on the AE must be submitted \leq 10 calendar days of learning of the AE.

¹ Serious adverse events that occur more than 30 days after the last administration of investigational agent/intervention and have an attribution of possible, probable, or definite require reporting as follows:

Expedited 24-hour notification followed by complete report \leq 5 calendar days for:

- All Grade 4, and Grade 5 AEs

Expedited 10 calendar day reports for:

- Grade 2 adverse events resulting in hospitalization or prolongation of hospitalization
- Grade 3 adverse events

Additional Instructions or Exclusions:

- All adverse events reported via CTEP-AERS (i.e., serious adverse events) should also be forwarded to your local IRB, according to local IRB policies.
- Alliance A091202 uses a drug under an Alliance IND. These reporting requirements apply for all agents (any arm) in this trial.
- Grade 3/4 myelosuppression or febrile neutropenia and hospitalization resulting from such do not require CTEP-AERS, but should be submitted as part of study results via routine reporting.
- Treatment expected adverse events include those listed in [Section 10.0](#), in the IB for efatutazone.
- All new malignancies must be reported through CTEP-AERS whether or not they are thought to be related to either previous or current treatment. All new malignancies should be reported, i.e. solid tumors (including non-melanoma skin malignancies), hematologic malignancies, myelodysplastic syndrome/acute myelogenous leukemia, and in situ tumors. In CTCAE v5.0, secondary malignancies may be reported as one of the following three options: 1) Leukemia secondary to oncology chemotherapy, 2) Myelodysplastic syndrome, or 3) Treatment-related secondary malignancy. Whenever possible, the CTEP-AERS reports for new malignancies should include tumor pathology, history or prior tumors, prior treatment/current treatment including duration, any associated risk factors or evidence regarding how long the new malignancy may have been present, when and how the new malignancy was detected, molecular characterization or cytogenetics of the original tumor (if available) and of any new tumor, and new malignancy treatment and outcome, if available.
- All pregnancies and suspected pregnancies occurring in female patients during therapy or within 28 days after completion of treatment on A091302 must be reported via CTEP-AERS. In CTCAE version 5.0, pregnancy loss is defined as “Death in utero,” and any pregnancy loss should be reported as “Pregnancy loss” under the Pregnancy, puerperium and perinatal conditions SOC (grade 4).
 - o CTEP-AERS reports should be amended upon completion of the pregnancy to report pregnancy outcome (e.g. normal, spontaneous abortion, therapeutic abortion, fetal death, congenital abnormalities). Fetal deaths should be reported as “Death neonatal” under the General disorders and administration SOC (grade 4).
 - o The CTEP-AERS report should be amended for any neonatal deaths occurring within 28 days of birth considered at least possibly related to treatment. Use the event term “Death neonatal” under the General disorders and administration SOC (grade 4).
- Death due to progressive disease should be reported as Grade 5 “Disease progression” in the system organ class (SOC) “General disorders and administration site conditions.” Evidence that the death was a manifestation of underlying disease (e.g., radiological changes suggesting tumor growth or progression: clinical deterioration associated with a disease process) should be submitted.
- The reporting of adverse events described in the table above is in addition to and does not supplant the reporting of adverse events as part of the report of the results of the clinical trial, e.g. cooperative group data reporting.

10.0 DRUG INFORMATION

10.1 Efatutazone dihydrochloride monohydrate (CS-7017) (Alliance IND #121997)

Procurement

Efatutazone dihydrochloride monohydrate (efatutazone) will be provided by Daiichi Sanyko and distributed by Biologics, Inc. Use the order form on the A091202 CTSU webpage to order efatutazone.

Formulation

Efatutazone is supplied as 0.25 mg tablets. The strength of efatutazone is expressed as the anhydrous free base. Efatutazone is supplied as white uncoated tablets. The inactive ingredients are mannitol, low-substituted hydroxypropyl cellulose, silicon dioxide, and magnesium stearate.

The uncoated tablets are provided in 100 ct amber glass bottles.

Preparation, Storage and Stability

All drug supplies should be stored in a secure location, at room temperature, up to 25°C (77°F), with excursions permitted from up to 30°C (86°F). At the end of the trial, any expired or remaining supplies should be destroyed according to institutional procedure.

Administration

Efatutazone should be taken twice daily at the same time each day, approximately 12 hours apart with or without food.

Drug Interactions

CYP3A4/5 is involved in the metabolism of efatutazone. Efatutazone may inhibit CYP2C8, CYP2C9, CYP2C19, and CYP3A4. A drug-drug interaction study with CYP3A4 inhibitor ketoconazole has been evaluated in healthy subjects. With concurrent administration of ketoconazole, total exposure of efatutazone increased by approximately 71% without significantly affecting the peak exposure.

Food and gastric pH effect have been evaluated in healthy subjects receiving efatutazone. No clinically significant effect was observed on the oral bioavailability of efatutazone by either food or gastric pH. Therefore, efatutazone can be taken together with food or gastric pH modifiers.

In vitro studies indicate that efatutazone has an inhibitory potential on uptake transporters (OATP1B1, OATP1B3, OAT3, and OCT2) and efflux transporters (P-glycoprotein and BCRP) with IC₅₀ values of 0.508 to 16µM. However, these levels of efatutazone are much higher than the exposure observed in humans; therefore drug-drug interaction on these transporters would be unlikely.

Pharmacokinetics

Absorption: Well absorbed and has high oral bioavailability (59-101.8%). The rate of absorption is slightly slower in the fed state compared to the fasted state with respective median t_{max} values of 3 and 2 hours. The 90% CI for the ratio of C_{max} for fed to fasted states was from 79.3% to 89.2% associated with a 15.9% decrease in mean C_{max}. Efatutazone may be taken without regard to meals.

Distribution: V_d: 16.9 L at 0.5 mg dose

Protein binding in humans is 99.52% and low partitioning into red blood cells.

Metabolism: In rats and monkeys efatutazone was mainly metabolized by O-dearylation followed by sulfation and glucuronidation. *In vitro* correlation analyses conducted using human liver microsomes and specific antibodies for each P50 isoform suggest that efatutazone is mainly metabolized by CYP3A4/5.

Half-life elimination: 8.37 hours

Excretion: Feces (69.9%); urine (20.2%)

Clearance: 1.45 L/hour

Adverse Events

Final safety data are available from 10 completed studies as of December 8, 2011. Adverse drug reactions which have a reasonable causal relationship to treatment with efatutazone include: edema, facial edema, localized edema, peripheral edema, pitting edema, fluid retention, weight gain, joint swelling, facial swelling, pleural effusions, hypercholesterolemia, hypertriglyceridemia, fatigue, asthenia, dyspnea, nausea, pain in the extremities, and anemia. Neutropenia and febrile neutropenia has been observed when efatutazone was given with FOLFIRI.

